12.13. Subject Monitoring

Subjects will be monitored for AEs throughout the study by the study unit staff. The principal investigator or designated sub-investigator will be on site for drug administration and until 6 hours after administration of study drug to the last subject. The principal investigator or designated sub-investigator will also be available (eg, “on call”) for the remainder of the treatment visit. If necessary, a physician, either at the study site or in a nearby hospital, will administer treatment for any AEs.

Safety parameters, including laboratory results, will be assessed by the principal investigator or his delegate using the site’s criteria for clinical laboratory acceptance ranges as suggested guidelines in making the medical assessment.

Scheduled safety measurements will be repeated according to appropriate SOPs or upon request from a physician. Any abnormal repeated measurement will be evaluated by a physician and repeated if judged necessary. Further action may be taken on the physician’s request.

Subjects will be advised to notify their health care professionals (eg, physician, dentist, and/or pharmacist) that they are participating in a clinical research study of a drug called PRAM9 before taking any medicines or undergoing any medical procedure.

13. DATA ANALYSIS AND STATISTICAL METHODS

13.1. General Approach

Detailed methodology for PK, PD, descriptive and inferential statistical analyses of the data collected in this study will be documented in the SAP.

Descriptive statistics will be used to summarize the clinical and laboratory data. Continuous data will be represented by number of subjects, mean, median, standard deviation (SD), and range, while categorical variables will be presented by number and percentage of subjects. Baseline values are determined by the last evaluable measurement before study drug injection in each treatment period. Point estimates may be derived with 2-sided 95% confidence intervals. An analysis of variance (ANOVA) will be performed to evaluate effect of study treatment and period. There is no reason to think that sequence will have an effect on the outcome.

13.1.1. Sample Size Calculation

Up to 21 subjects will be qualified for the study and will complete the overnight stay as part of Visit 2 to ensure that 18 total subjects are randomized to a study treatment sequence. The target of 18 randomized subjects is considered sufficient to allow an initial evaluation of PK/PD response and safety of these novel pramlintide-insulin formulations. Formal sample sizes were not conducted.

13.2. Primary Endpoint Analysis

All PK/PD analyses will be performed using the PK/PD analysis population.

The following variable will be compared among the treatments for PD purposes:

- AUC₀₋₁₈₀ (mg/dL × minutes) for plasma glucose > 180 mg/dL

13.3. Secondary Endpoint Analysis

13.3.1. Safety Endpoints

All safety analyses will be performed using the safety population.

The following variables will be compared between the treatments for safety purposes:

- Incidence of AEs and SAEs
- Change from baseline in laboratory safety variables
- Change from baseline in vital sign measurements
- Change from baseline in body weight
- Local tolerability assessments, including:
 - Incidence of erythema and or edema formation at site of injection assessed using the Draize scale ([Appendix 1](#)).
 - Subjective injection site discomfort as reported by subjects using a 11-point NRS ([Appendix 2](#)).

13.3.2. Pharmacodynamic and Pharmacokinetic Endpoints

All PK/PD analyses will be performed using the PK/PD analysis population.

The following variables will be compared between the treatments for PD and PK purposes:

- Mean proportional time with plasma glucose > 180 mg/dL for 0-180 minutes
- Mean proportional time after glucose challenge for plasma glucose levels between 126 to 180 mg/dL
- Mean proportional time* for plasma glucose < 70 mg/dL
- Mean proportional time* for plasma glucose < 54 mg/dL
- Mean proportional time* for plasma glucose > 180 mg/dL
- Mean proportional time* for plasma glucose > 250 mg/dL
- AUC_{0-360} (mg/dL \times minutes) for plasma glucose > 180 mg/dL
- AUC_{0-360} (mg/dL \times minutes) for plasma glucose > 250 mg/dL
- AOC_{0-360} (mg/dL \times minutes) for plasma glucose < 70 mg/dL
- AOC_{0-360} (mg/dL \times minutes) for plasma glucose < 54 mg/dL
- Plasma glucose C_{max} and T_{max}
- Plasma levels ($AUC_{0-90\ min}$, $AUC_{0-180\ min}$, $AUC_{0-360\ min}$, C_{max} , and T_{max}) for both insulin and pramlintide

* Mean proportional time during 0 to 360 minutes post-injection of study drug.

13.4. Adverse Events

All safety analyses will be performed using the safety analysis population. TEAEs will be summarized using the Medical Dictionary for Regulatory Activities (MedDRA[®]) system organ class (SOC) and preferred term (PT), classified from verbatim terms. Listings of all AEs (including non-TEAEs), treatment-emergent SAEs, and TEAEs leading to study drug discontinuation will be provided by treatment group, subject, verbatim term, MedDRA SOC and PT, start and end dates, seriousness, severity, relationship to study drug, action taken with study treatment, frequency, and outcome.

AEs will be summarized overall by the number and percentage of subjects who experienced at least one AE of the following categories in each treatment group: any AE, any TEAE, any drug-related TEAE, any severe or life-threatening TEAE, any serious TEAEs, any drug-related SAE, any SAE leading to death, any TEAE leading to premature discontinuation of study drug, and any SAE leading to premature study drug discontinuation.

The number and percentage of subjects reporting a TEAE in each treatment group will be tabulated by SOC and PT; by SOC, PT, and severity (mild, moderate, and severe/life-threatening/death); and by SOC, PT, and relationship (unrelated or related to study drug).

The numbers and percentages of subjects reporting an SAE or reporting a TEAE leading to premature discontinuation of study drug in each treatment group will be summarized by SOC and PT.

13.5. Laboratory Safety Assessments

Laboratory values will be flagged if outside the normal range. A listing of clinically significant abnormal values will be presented. The individual values will be listed indicating values outside normal range. Laboratory assessments will be summarized at Screening and at the end of the study. Significant deviations/changes from the Screening Visit to the Follow-Up Visit will be documented as AEs if the investigator judges these as being clinically significant.

13.6. Physical Examination

Subjects with any findings in the PE evaluation at Screening will be listed on the Medical History CRF. Changes to PE from Screening to end of trial will be recorded as AEs if they meet the definition of an AE or if the investigator judges these changes as being clinically significant.

13.7. Vital Signs and Body Weight

Vital signs will be summarized by descriptive statistics. Changes from pre- to post-dosing at each of the Treatment Period Visits will be conducted. If there are changes that meet the definition of an AE or if the investigator judges these as being clinically significant, they will be recorded on the eCRF as an AE.

Observed values as well as change from baseline data will be summarized descriptively in tabular format. The pre-study drug collections of vital signs at each Treatment Period will be considered as baseline.

13.8. Electrocardiogram

Any clinically significant ECG results will be recorded and followed as appropriate. The investigator's evaluations will be summarized in a data listing.

13.9. Local Tolerability

The incidence of any injection site discomfort (score > 0 on the ordinal rating scale) will be analyzed descriptively. The incidences of erythema and edema will be analyzed in a similar manner. Descriptive statistics will be provided for time of onset and duration (of discomfort) and discomfort description (ie, pain, irritation, itching, etc.).

Mean NRS scores will be compared between the treatments.

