11.3.5. Local Tolerability

Local tolerability will be assessed at Visits 2, 3, and 4 as follows:

- The investigator will use the modified Draize scale ([Appendix 1](#)) to assess erythema and edema formation at the injection site at 30, 90, and 360 minutes (\pm 2 minutes) after injection of study drug(s). If any scores remain > 1 at the 360-minute evaluation, the subject may leave the clinic but will be instructed to contact a study staff member if the condition fails to resolve. Every effort should be made to ensure that the same investigator will assess the injection sites on the subject at each visit.
- Subjects will complete a 11-point Numeric Rating Scale (NRS) questionnaire regarding injection site discomfort 10 and 30 minutes (\pm 2 minutes) after injection of study drug ([Appendix 2](#)). Question Q1c is to be answered at 360 mins post-study drug injection.

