Appendix 2. INJECTION SITE DISCOMFORT ASSESSMENT

[figure not shown]
Numeric Rating Scale (NRS) for Injection Site Discomfort

Investigative Site Instructions: The subject should complete the 11-point NRS for Injection Site Discomfort at 10 and 30 minutes (\pm 2 minutes) after injection of study drug. The subject will complete the NRS by drawing a circle around the number corresponding to the perceived intensity (severity) of discomfort according to the instructions below. The goal is for the subject to report the amount of discomfort, if any, remaining at each time point, as opposed to reporting the transient pain associated with needle insertion.

Note: If a subject is unable to physically complete the questionnaire, the subject will indicate the number on the NRS corresponding to their level of discomfort, and study staff will circle it. Documentation will be provided on each completed questionnaire as to who completed the form.

Subject Instructions: Ignoring any pain from insertion of the needle, please draw a circle around the number on the scale below that corresponds to the intensity (severity) of any discomfort you are feeling **right now** at the study drug injection site.

For example, if you are currently feeling no discomfort, you should circle the number “0” on the left end of scale. If you are currently feeling the worst discomfort possible, you should circle number “10” on the right end of the scale.

Injection Site Discomfort Description and Duration Questionnaire

Study Personnel Instructions: Question 1a should be completed by the subject at **10 ± 2** minutes after injection of study drug. If response is anything other than “None,” the subject should also answer Question 1b. All subjects should also answer Question 1c at 30 ± 2 minutes post-injection.

The goal is for the subject to report the qualitative nature and duration of discomfort, if any, associated with injection of study drug, ignoring any transient pain associated with needle insertion.

Note: If a subject is unable to physically complete the questionnaire, the subject will provide verbal responses, which will be recorded on the questionnaire by study staff. Documentation will be provided on each completed questionnaire as to who completed the form.

Subject Instructions: Please answer question 1a and 1c, and, if applicable to you, question 1b. In answering these questions, you should ignore any pain from insertion of the needle.

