1a. How would you describe any discomfort you felt from the study drug? (Check all that apply):

- None (Please ignore question 1b.)
- Pain (eg, throbbing, soreness, muscle ache)
- Itching
- Tingling, twitching, or numbness
- Irritation (eg, burning, stinging)

Other or additional comments: _____

1b. About how long did the discomfort last after the injection? (Check one):

- Less than 1 minute
- 1-2 minutes
- 3-5 minutes
- 6-9 minutes
- at least 10 minutes (Please complete question 1c before leaving the clinic.)

1c. In total, how long did the discomfort last after the injection? (Please enter a number below):

_____ Minutes

Reference:

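### The incidence of any injection site discomfort is taken from a scale that records only discomfort still present at 10 and 30 minutes, so discomfort that ended before the first reading counts as none

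*Protocol*

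**What the plan says.** Section 13.9 gives the case definition in parentheses: "The incidence of any injection site discomfort (score > 0 on the ordinal rating scale) will be analyzed descriptively". The same section also plans descriptive statistics for the onset, duration and type of discomfort, and a comparison of mean NRS scores between treatments.

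Section 13.3.1 lists the corresponding safety variable as "Subjective injection site discomfort as reported by subjects using a 11-point NRS". Section 11.3.5 schedules the NRS "questionnaire regarding injection site discomfort 10 and 30 minutes" after injection, with a 2-minute window either side, and Appendix 2 repeats the timing: "The subject should complete the 11-point NRS for Injection Site Discomfort at 10 and 30 minutes".

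Appendix 2 also says what the score means. For site staff: "The goal is for the subject to report the amount of discomfort, if any, remaining at each time point". For the subject: "if you are currently feeling no discomfort, you should circle the number" 0.

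A separate questionnaire in Appendix 2 asks about discomfort since the injection. Question "1a. How would you describe any discomfort you felt from the study drug? (Check all that apply") offers None or several types. Question "1b. About how long did the discomfort last after the injection? (Check one") offers five durations: less than 1, 1-2, 3-5, 6-9, and at least 10 minutes. Question 1a is answered at 10 ± 2 minutes, and 1b follows if the answer is not None.

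**The concern.** The label in Section 13.9 promises the share of subjects with *any* discomfort. The rule delivers the share with discomfort still present when the scale is filled in. These differ for anyone whose discomfort is brief, and the protocol plainly expects brief discomfort: four of the five answers to 1b are shorter than 10 minutes, and 1a lists burning and stinging.

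Local tolerability is a listed secondary safety endpoint, to be compared between treatments, for a new co-formulation. Section 12.2 keeps injection site reactions out of the adverse event data unless a skin reaction or pain needs medical intervention, so the adverse event tables will seldom supply the missing cases. A reader who takes the Section 13.9 incidence at its label would think discomfort less common than the subjects reported.

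**Working it through.** The protocol states no figure to reproduce. The check sets the definition against the instrument.

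**Which scale is meant.** Section 13.9 speaks of an ordinal rating scale. The modified Draize scale (Appendix 1) scores only erythema and edema, and questions 1a to 1c carry no score. The 11-point NRS is the only candidate, and Section 13.3.1 names it.

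**The rule applied to three illustrative records.**

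| Subject | 1a | 1b | NRS at 10, 30 min | Counted under 13.9 | Discomfort by 1a |
|---|---|---|---|---|---|
| A | Pain | 3-5 min | 0, 0 | No | Yes |
| B | Irritation | at least 10 min | 3, 0 | Yes | Yes |
| C | None | – | 0, 0 | No | No |

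Subject A is misclassified. A also appears in the description and duration summaries with pain lasting 3-5 minutes, so two results from one section disagree.

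**Effect of the window.** The first reading may fall between 8 and 12 minutes. The first three 1b categories end before any permitted reading. The 6-9 minute category ends before the nominal reading but can overlap one taken at 8 minutes. The exact statement is therefore that discomfort ending *before the first NRS reading* is lost.

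**Direction for one treatment.** Let p be the true share with any discomfort and f the share of those whose discomfort ended before the first reading. Then

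counted incidence = p × (1 − f) ≤ p.

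At an assumed p = 9/18 = 50%:

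- f = 0.25: 0.50 × 0.75 = 37.5%
- f = 0.50: 0.50 × 0.50 = 25%
- f = 0.75: 0.50 × 0.25 = 12.5%

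**Direction for a contrast.** Suppose, purely as an illustration, that duration is exponential with mean m minutes. The share still scoring above 0 at 10 minutes is exp(−10/m):

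- m = 3: 0.036
- m = 5: 0.135 (0.202 for a reading at 8 minutes, 0.091 at 12)
- m = 10: 0.368

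*Same duration distribution in both treatments, true 60% versus 35%, a difference of 25 points.* The counted difference is 25 × 0.036 = 0.9, 25 × 0.135 = 3.4 or 25 × 0.368 = 9.2 points. The contrast narrows.

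*Same true incidence of 50%, mean duration 10 versus 3 minutes.* The counted figures are 0.50 × 0.368 = 18.4% and 0.50 × 0.036 = 1.8%. A true difference of zero becomes about 17 points. The contrast widens.

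The sign of the error for a single treatment is fixed; its sign for a contrast is not.

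**The case against.** The best defence is that the rule fits the declared variable. Section 13.3.1 lists discomfort as reported on the NRS, a score above 0 is its natural incidence summary, and Appendix 2 deliberately aims at remaining discomfort so as to set aside needle pain. On that view the fault is one loose word, and adding 1a creates a different, composite measure. This stands in part: an NRS-based line is legitimate if labelled as discomfort present at 10 or 30 minutes. It does not rescue the present label. Nor is the delay needed to exclude needle pain, because the questionnaire containing 1a also tells subjects to ignore it.

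A second defence is that brief discomfort is already reported in the description and duration summaries. That is true and lowers the consequence: a reader might infer that these data are lost, and they are not. The incidence figure remains wrong for its label and would disagree with those summaries.

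A third is that Section 13.1 leaves detailed methods to the SAP. The SAP could settle the derivation and labelling, but Section 13.9 does not leave the case definition open; it fixes one that conflicts with Appendix 2.

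**Conclusion.** The point holds as a definition that does not match its label. Taking subjects' answers at face value, each treatment's incidence of any discomfort can only be understated. The contrast between treatments combines incidence with persistence and can move either way.

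Three stronger readings are tempting and not supported:

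- *Every subject whose discomfort ended within 10 minutes is missed.* The ±2-minute window allows a reading at 8 minutes, which can catch discomfort ending between 8 and 10 minutes.
- *Treatment differences shrink toward zero.* This requires similar durations across treatments, which the protocol does not establish; the example with unequal durations goes the other way.
- *A headline result is compromised.* The protocol gives this figure no such rank. It is descriptive, and no sample size calculation depends on it.

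The amount of understatement is unknown. All incidences, early-ending shares and mean durations above are assumptions. The four short 1b categories show that brief discomfort was foreseen, not how often it occurs. Severity is minor to moderate.

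**What to change.** In Section 13.9, and in the SAP to match:

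1. Define the incidence of any injection site discomfort, per treatment, as question 1a answered other than None, or NRS above 0 at 10 or 30 minutes.
2. Report NRS above 0 at each time on separate lines, labelled residual discomfort at 10 minutes and at 30 minutes.
3. Replace the reference to an ordinal rating scale with the 11-point NRS.

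The cost is about a sentence of text. Question 1a is already collected at 10 minutes at every dosing visit, so no procedure or form changes. In the illustration, the new definition would count the full 50% whatever the early-ending share. The small downside is a higher, less favourable reported incidence.

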13.10. Prior and Concomitant Medications

Prior and concomitant medications will be mapped to a World Health Organization (WHO) drug classification. The number and percent of subjects taking concomitant medications will be summarized.

13.11. Subgroup Analysis

No subgroup analyses are planned.

13.12. Demographics and Baseline Characteristics

Demographics and baseline characteristics will be summarized for all subjects overall and by Treatment Period. Summary statistics (eg, number of subjects, mean, median, SD and range) will be generated for continuous variables (eg, age and weight) and the number and percentage of subjects within each category will be presented for categorical variables (eg, sex, ethnicity, and race).

13.13. Subject Disposition

A detailed description of subject disposition will be provided and will include the following:

- A summary of overall subject enrollment status (consented, screened, screen failures, randomized, replaced)
- A summary of subjects who discontinued the study
- An account of identified protocol deviations

All subjects who are consented for the study will be accounted for in the summation. The number of subjects who do not qualify for certain analysis populations and who did not complete all 3 treatment periods will also be summarized.

14. DATA HANDLING, RECORD KEEPING, MONITORING AND AUDITS

14.1. Case Report Forms/Electronic Data Record

Data collection is the responsibility of the clinical study staff under the supervision of the investigator. During the study, the investigator will maintain complete and accurate documentation for the study.

As defined in the ICH Guidelines for Good Clinical Practice (E6(R2)), Section 1.52, source documents may include: original documents, data, and records (eg, hospital records, clinical and office charts, laboratory notes, memoranda, participant's diaries or evaluation checklists, pharmacy dispensing records, recorded data from automated instruments, copies, or transcriptions certified after verification as being accurate and complete, microfiches, photographic negatives, microfilm or magnetic media, X-rays, participant files, and records kept at the pharmacy, at the laboratories, and at medico-technical departments involved in the clinical study).

As used in this protocol, the term CRF is understood to refer to an electronic data record, ie, an eCRF. An eCRF is required and should be completed for each individual subject. The completed original eCRFs are the property of Xeris Pharmaceuticals and should not be made available in any form to third parties, except for authorized representatives of Xeris Pharmaceuticals or appropriate regulatory authorities, without written permission from Xeris Pharmaceuticals.

Queries generated by Data Management and within the EDC will be sent to the study site for resolution. The investigator is responsible for the review and approval of all responses to eCRF queries.

14.2. Record Retention

To enable evaluations and/or audits from regulatory authorities or Xeris Pharmaceuticals, the investigator agrees to keep records, including the identity of all participating subjects (sufficient information to link records, eg, eCRFs and hospital records), all original signed informed consent documents, copies of all eCRFs, safety reporting forms, source documents, and detailed records of treatment disposition, and adequate documentation of relevant correspondence (eg, letters, meeting minutes, telephone calls reports). The records should be retained by the investigator according to the ICH, local regulations, or as specified in the Clinical Study Agreement, whichever is longer. The investigator must obtain Xeris Pharmaceuticals' written permission before disposing of any records, even if retention requirements have been met.

14.3. Monitoring

Monitoring and auditing procedures developed by Xeris Pharmaceuticals and/or its designee will be implemented to ensure compliance with FDA and ICH GCP and Good Laboratory Practices (GLP) guidelines.

The Xeris Pharmaceuticals' designated representative (the monitor or auditor) will contact the investigator and conduct regular visits to the clinical site. The monitor will be expected and

allowed to verify the investigator's qualifications, to inspect clinical site facilities, and to inspect study records, including proof of IRB/IEC review, with the stipulation that subject confidentiality will be maintained in accordance with local and federal regulations, including Health Insurance Portability and Accountability Act (HIPAA) requirements. The monitor will also be responsible for confirming adherence to the study protocol, inspecting eCRFs and source documents, and ensuring the integrity of the data. eCRFs will be checked for accuracy, completeness, and clarity and will be cross-checked for consistency with source documents, including laboratory test reports and other subject records. Instances of missing or uninterpretable data will be resolved in coordination with the investigator.

The monitor/auditor will also investigate any questions concerning adherence to regulatory requirements. Any administrative concerns will be clarified and followed. The monitor will maintain contact with the site through frequent direct communications with the study site by email, telephone, facsimile, and mail. The investigator and all other site personnel agree to cooperate fully with the monitor and will work in good faith with the monitor to resolve all questions raised, and difficulties detected by the monitor.

